7.3.1 Missing data analysis methods

Not Applicable.

8 STATISTICAL METHODS

8.1 General statistical conventions

All data analyses will be performed using the SAS® software package version 9.3 or higher.

In general, continuous variables will be summarized using the following standard descriptive summary statistics: number of observations, arithmetic mean, standard deviation, minimum, lower quartile, median, upper quartile, maximum. Categorical data will be described using count and frequency. Percentages will be rounded to one decimal place. Shift tables will be provided, where appropriate.

All analyses and summaries will be presented by treatment group, unless otherwise specified.

The following international dictionaries (in latest available version) will be used for medical coding:

- Diagnoses: Medical Dictionary for Regulatory Activities (MedDRA) v18.1
- Medications: World Health Organization (WHO) Drug Dictionary including Anatomical Therapeutic Chemical (ATC) classification Sept 2014
- AEs: MedDRA v18.1

All patient data, including those derived, will be presented in individual patient data listings. Unless otherwise stated, unscheduled visit results will be included in date/time chronological order, within patient listings only. All listings will be sorted by investigational site, patient number, date/time and visit. The actual treatment group as well as patient's sex and age will be stated on each listing. Unless otherwise stated, data listings will include all patients in Safety population.

8.2 Patient disposition

Patient disposition information will be summarized by treatment group and overall. The number of patients screened, the number and percent of patients who are screen failure, randomized, who took a dose of study drug, who were randomized and not treated, who complete the study and who withdraw early from the study will be presented. Screen failure percentage is calculated from number of screened patients and other percentages are calculated among number of randomized patients. Patients from Safety Population will be summarized using descriptive statistics displaying number and percentage. Percentage will be done using the number of randomized as denominator.

The primary reason for early withdrawal will also be summarized by treatment group in Safety Population.

Patient disposition will be listed for all patients screened.

Treatment Misallocations:

If a subject was:

- Randomized but not treated, they are by definition excluded from the safety analyses as not receive at least of one dose of study drug.
- Randomized but took incorrect treatment, then they will be reported under the treatment they actually received for all safety analyses.

8.3 Protocol deviations

A listing will include the inclusion/exclusion criteria violated at Screening/Randomization as well as other protocol deviations identified based on data recorded on the eCRF and/or protocol deviation Logs from [REDACTED] Medical for all randomized patients.

Major protocol deviations defined as below will be listed separately:

- Lack of compliance defined as having administered <75% or >125% of the scheduled doses for the specified duration of the study
- Completion of the TOC/EOS Visit outside the specified visit window (Study Day 5 \pm 1 day) (if patient did not discontinue the study due to lack of treatment effect or worsening of the underlying condition requiring alternate or supplemental therapy).

8.4 Demographics and baseline characteristics

8.4.1 Demographics

Age, height, weight, BMI, the number of formed stools in the past 24 hours at baseline, the number of unformed stools in the past 24 hours at baseline, and the duration (days) in the host country will be summarized descriptively. Sex, Race, Ethnicity, country of residence, signs and symptoms of enteric infection (abdominal pain or cramps, nausea, vomiting,

fecal urgency, gas/flatulence, and tenesmus), and pathogen status (inflammatory/invasive pathogens, diarrheagenic *E Coli* group without evidence of inflammatory/invasive pathogens, other pathogens without evidence of inflammatory/invasive pathogens) at baseline will be summarized. Safety population will be used for reporting.

8.4.2 Medical history

Listing for medical history will be presented by system organ class (SOC) and preferred term (PT) Medical Dictionary for Regulatory Affairs® (MedDRA) Version 19.0 or higher.

8.4.3 Prior and concomitant medications

Prior medications are defined as those medications with a start date prior to the first dose of study drug. Concomitant medications are defined as those medications with a start date on or after the first dose of study drug. Prior medications were recorded in medical history at the Screening/Randomization visit. The administration of any concomitant medication or herbal/dietary supplements during the study will be recorded by patients on the Supplemental Form provided at the Screening/Randomization Visit. The form will be reviewed by the Investigator during the call on Study Day 3 and at the TOC/EOS Visit. Prior and concomitant medications will be recorded on the eCRF by the investigator. Prior and concomitant medications used in this study will be coded by using the latest available version of the World Health Organization (WHO) Drug Dictionary including Anatomical Therapeutic Chemical (ATC) classification.

Listing for prior and concomitant medications will be presented.

8.5 Extent of exposure

8.5.1 Treatment duration

At TOC/EOS Visit, the date/time of first dose and last dose, in addition to the actual total number of tablets taken will be recorded in the eCRF. Duration of study drug (in hours) will be the date/time of last dose – date/time of first dose rounded to hours.

Study drug exposure will be summarised by treatment group on the Safety Population using descriptive statistics.

The actual total number of tablets taken will be summarized by treatment group using descriptive statistics.

8.5.2 Treatment compliance

Treatment compliance in this study will be monitored by tablet count as described in section 7.1.

Summary of treatment compliance will be presented by treatment group by the number of subjects (n), mean, standard deviation, median, min, and max. They will also be summarized in categories “< 75%”, “75-125%” and “> 125%” using frequency tables.

Treatment compliance will be summarized and listed based on the Safety Population.

8.6 Safety analyses

All definitions relative to safety endpoints are detailed in Section 7.2.1

Safety analyses will be conducted on the Safety Population (treated patients) and will be performed for all safety variables specified below.

All safety data will be summarized by treatment group and overall.

The safety analyses of changes from baseline to a specific time point in safety variables (e.g., laboratory parameters, vital signs, and physical examination) will only include patients from the Safety Population who have data available for both the baseline and the time point under consideration unless otherwise specified.

No statistical test will be performed.

8.6.1 Adverse events

All Adverse events (AEs) will be classified by System Organ Class (SOC) and Preferred Term (PT) according to the Medical Dictionary for Regulatory Activities (MedDRA) Version 19.0 or higher.

Incidences of Treatment-Emergent Adverse Events (TEAEs) will be tabulated by SOC and PT. Incidences of TEAEs will also be presented by maximum severity (intensity), seriousness and relatedness to study drug. Subjects who discontinued due to AEs will be summarized by SOC and PT in a separate table. Patients are counted only once in each SOC, and only once in each PT category. The table will be sorted in alphabetical order by SOC and in decreasing frequency of PT based on total reports within each SOC.

In summary, the following tables will be developed for summarizing AEs.

- Overall summary of TEAEs, it includes number and percentage of subjects with any TEAEs, subjects with any treatment-emergent SAE, subjects with any severe TEAEs, subjects with any treatment-related TEAEs, subjects with TEAEs leading to study discontinuation, subjects with death.
- Summary of TEAEs by SOC and PT
- Summary of treatment-emergent SAEs by SOC and PT
- Summary of TEAEs by SOC and PT and maximum severity
- Summary of TEAEs by SOC and PT (treatment-related)
- Summary of treatment-emergent SAEs by SOC and PT (treatment-related)

- Summary of TEAEs by SOC and PT and maximum severity (treatment-related)
- Discontinuations due to TEAEs by SOC and PT
- Death due to TEAEs by SOC and PT

In addition, an overall summary for the categories above will be prepared by treatment group and overall.

Individual patient data listings will be provided for those with non-treatment emergent AEs, TEAEs, treatment-emergent SAEs, treatment-related TEAEs, deaths, and discontinuation due to AEs.

Regarding the summaries by severity and causality the following rule will be applied: if a patient experiences more than one AE within the same SOC or with the same preferred term, the AE with the highest severity or closest relationship to study treatment will be used for the analysis.

8.6.2 Clinical laboratory evaluations

Laboratory data will be subjected to both a quantitative analysis (descriptive summary statistics) and qualitative analysis where frequencies of normal, abnormal low, and abnormal high values will be computed.

Hematology, blood chemistry and urine samples will be collected at Screening/Randomization Visit and TOC/EOS Visit. Urine pregnancy test will be done on all females of child bearing potential (not post-menopausal or not surgically sterile) prior to randomization at Screening/Randomization Visit and at TOC/EOS Visit. If a subject has repeated laboratory values for a given time point, the value from the last evaluation will be used. For the purposes of summarization in both the tables and listings, all laboratory values will be presented in SI units. If a lab value is reported using a nonnumeric qualifier e.g., less than (<) a certain value, or greater than (>) a certain value, the given numeric value will be used in the summary statistics, ignoring the nonnumeric qualifier.

Please refer to protocol section 12.4 for detailed list of parameters collected in blood samples for analyses. Summary statistics of measurements, change from baseline values, percent change from baseline values for hematology, chemistry, and urinary parameters will be presented at Screening/Randomization Visit and TOC/EOS Visit by treatment group. Shift tables displaying changes with respect to the normal range between baseline and TOC/EOS Visit will be provided. A listing of all subjects with abnormal values at any time point will be given.

8.6.3 Vital signs

Vital signs (body temperature, blood pressure, heart rate, respiratory rate) will be measured at Screening/Randomization Visit, TOC/EOS Visit and unscheduled visit. Vital

sign measurements at baseline and TOC/EOS Visit, and change at TOC/EOS Visit from baseline will be summarized by visit and treatment group.

A patient data listing of all clinically significant abnormal vital signs, including findings from unscheduled visits, will be provided.

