13.2 Statistical Methods

A detailed description of all statistical analyses to be performed for this study will be given in a statistical analysis plan (SAP). Any deviations from the analysis detailed in the protocol will be described in the SAP.

No interim analysis is planned.

Any deviations from the original SAP will be described and justified in the final CSR, as appropriate.

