13.2.7.2 Vital Signs

Vital signs (body temperature, blood pressure, heart rate, respiratory rate) will be analyzed in the following way:

- Standard descriptive summary statistics will be calculated at each scheduled time point and the last individual time point.
- Further, standard descriptive summary statistics will be computed for the absolute change from baseline to each scheduled time point after baseline and the last individual time point.
- A patient data listing of all clinically significant abnormal vital signs will be provided.

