13.2.7.3 Laboratory Parameters

Laboratory data will be subjected to both a quantitative analysis (descriptive summary statistics) and qualitative analysis where frequencies of normal, abnormal low, and abnormal high values will be computed.

The following analyses will be performed:

- Standard descriptive summary statistics will be calculated at each scheduled measuring time point and the last individual measuring time point.
- Standard descriptive summary statistics will be calculated for the absolute and relative change from baseline to each scheduled measuring time point after baseline and the last individual measuring time point.
- Shift tables displaying changes with respect to the normal range between baseline and each scheduled measuring time point after baseline and the last individual measuring time point will be provided.
- A listing of all patients with abnormal values at any time point will be given.

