9 CHANGES TO PLANNED ANALYSIS FROM STUDY PROTOCOL

 This SAP v1.0 excludes efficacy analyses from the final analyses due to low number of randomized patients.

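### SAP 8.6.3 (and, with less practical effect, 8.6.2) omits the protocol's last-individual-time-point safety summaries, and SAP Section 9 does not declare the omission

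*SAP*

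**What the plan says.** **Protocol, vital signs (13.2.7.2).** "Standard descriptive summary statistics will be calculated at each scheduled time point and the last individual time point". Changes are planned in the same way, as "the absolute change from baseline to each scheduled time point after baseline and the last individual time point".

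**Protocol, laboratory (13.2.7.3).** The same pair of time points is used for values, for absolute and relative changes, and for shift tables, where changes against the normal range from baseline to "each scheduled measuring time point after baseline and the last individual measuring time point will be provided".

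**SAP, vital signs (8.6.3).** "sign measurements at baseline and TOC/EOS Visit, and change at TOC/EOS Visit from baseline will be summarized by visit and treatment group". The same section expects vital signs to be taken at unscheduled visits too.

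**SAP, laboratory (8.6.2).** Measurements, changes and percent changes "will be presented at Screening/Randomization Visit and TOC/EOS Visit by treatment group". For shifts: "Shift tables displaying changes with respect to the normal range between baseline and TOC/EOS Visit will be provided".

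**Declaring changes.** Protocol 13.2: "Any deviations from the analysis detailed in the protocol will be described in the SAP". The only change named in SAP Section 9 is this: "This SAP v1.0 excludes efficacy analyses from the final analyses due to low number of randomized patients".

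**The concern.** TOC/EOS is the only scheduled post-baseline assessment of vital signs and laboratory tests. A separate last-value row therefore adds information only for patients whose last value is not the TOC/EOS value. Those are the patients the SAP tables leave out.

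The protocol gives a route to such patients. Under 9.1.2.4, someone who is worse at the Day 3 call may be recalled to the site. Under 9.3.3, someone who needs other therapy is discontinued. Patients without a TOC/EOS value could thus include some of the sickest, and tables limited to TOC/EOS would describe those who stayed.

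Changes in vital signs and laboratory parameters are named safety endpoints (SAP 4.3), and safety is all that this SAP still analyses. A reader of Section 9 would not learn that a planned safety summary had gone. The reason given there for dropping efficacy, the low number of patients, does not explain a cut in descriptive safety tables.

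**Working it through.** There is no stated figure to reproduce. The check compares the two texts and then follows one patient through them.

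**Step 1: count the summary types each text specifies, per parameter.** B is baseline, T is TOC/EOS and L is the last individual time point.

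| | Protocol | SAP | Dropped |
|---|---|---|---|
| Vital signs: value | B, T, L = 3 | B, T = 2 | 1 |
| Vital signs: change | T, L = 2 | T = 1 | 1 |
| Laboratory: value | B, T, L = 3 | B, T = 2 | 1 |
| Laboratory: absolute change | T, L = 2 | T = 1 | 1 |
| Laboratory: relative change | T, L = 2 | T = 1 | 1 |
| Laboratory: shift | T, L = 2 | T = 1 | 1 |
| **Total** | **14** | **8** | **6** |

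Vital signs go from 5 to 3 and laboratory data from 9 to 5. None of the six is declared in Section 9.

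**Step 2: look for another SAP rule that brings the values back.**
- SAP 8.1 sends unscheduled results to patient listings only, unless otherwise stated. Neither 8.6.2 nor 8.6.3 states otherwise for the tables.
- SAP 7.3 does not impute missing safety data.
- SAP 8.6 limits change analyses to patients with data at both baseline and the time point in question.
- The rule on repeated laboratory values in 8.6.2 applies within a given time point.
- SAP Appendix B on visit windows is marked not applicable, so no stated rule assigns an early assessment to TOC/EOS.

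**Step 3: follow a patient with a baseline value, an unscheduled post-dose value and no TOC/EOS value.** Read the protocol's term as the last available post-dose value. Under the protocol, the unscheduled value enters the by-arm last-value summary, the change and, for laboratory data, the shift table. Under the SAP, it enters no by-arm post-baseline summary, change or shift table.

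**Step 4: illustrate the size, on assumed numbers.** The documents do not say how many patients were randomized. Suppose one patient of n in an arm leaves with an unscheduled temperature 1.5 °C above baseline and no TOC/EOS value, and nobody else changes. The SAP's mean change is 0.00 °C. The protocol's last-value row would show 1.5/n:
- n = 5: 1.5/5 = 0.30 °C
- n = 10: 1.5/10 = 0.15 °C
- n = 20: 1.5/20 = 0.075 °C

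If every treated patient has a TOC/EOS value and none later, the last-value row equals the TOC/EOS row and the difference is 0.

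**The case against.** The case for leaving the SAP alone is substantial.

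- **Few patients, perhaps none, are affected.** Protocol 9.3.3 asks for the TOC/EOS procedures at withdrawal where possible, and a patient recalled to the site is well placed to have them. A patient never seen again has no post-dose site value, so the protocol's row would miss that patient too. The gap needs someone who attends an unscheduled visit, has values taken, has no assessment recorded as TOC/EOS, and does not return. The documents do not show that such a patient exists. This stands, and it limits the size of the point.
- **The laboratory half has little behind it.** SAP 8.6.2 names only two collection visits, whereas 8.6.3 names unscheduled ones. This also stands. The laboratory omission is the same departure from the protocol, but it matters less in practice.
- **The values are reported elsewhere.** They are in the listings, with treatment group shown. Clinically significant vital signs, including unscheduled ones, and abnormal laboratory values have their own listings. Abnormalities that lead to stopping treatment, or that the investigator judges reportable, become adverse events under protocol 12.1.9 and so reach the by-arm tables. No safety tests are planned. In very small arms a listing may tell more than a mean.
- **The term is undefined.** The protocol does not say that the last individual time point includes unscheduled visits. That is the natural reading, because otherwise the row would only repeat TOC/EOS, but it is an inference.
- **The table shells are a separate document** and could still contain the row.

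None of this answers the departure itself: the protocol specifies the summaries, the SAP text omits them, and Section 9 is silent.

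A reader might infer more than the documents support. The affected patient does not vanish from every by-arm table: baseline, exposure, disposition and treatment-emergent adverse-event tables still count that patient. Nor does the 6-of-14 count measure lost information, since most of those rows would repeat TOC/EOS.

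**Conclusion.** The point holds as an undeclared departure from the protocol's safety analysis, clearest for vital signs and of less practical effect for laboratory data. The omission and the silence in Section 9 can be read directly from the text and do not depend on the data.

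The consequence for results rests on two assumptions: that the last individual time point means the last available post-dose value, and that at least one treated patient has such a value other than at TOC/EOS. If both hold, a patient with no TOC/EOS value is missing from the by-arm post-baseline vital-sign (or laboratory) tables, and in a small arm one such patient could visibly move a mean. If the second fails, nothing in the tables changes. The likely effect is small. The documents do not support a claim that the safety conclusions are distorted or that abnormal values go unreported.

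**What to change.** In SAP 8.6.3 and 8.6.2, restore a last-individual-time-point row by treatment group for values and changes, and for shifts in the laboratory tables. Define it as the last non-missing value after the first dose, including unscheduled and early-withdrawal visits. State whether an early-withdrawal assessment is tabulated in that row or as TOC/EOS. If the sponsor prefers to leave the row out, declare that in Section 9 with a reason.

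The cost is SAP wording and one extra row in tables already planned, from data already collected. The downside is that the row will mostly repeat TOC/EOS. If no treated patient lacks a TOC/EOS value or has a later one, a sentence in Section 9 is enough.

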8.6.4 Physical examinations

Physical examinations will be performed at Screening/Randomization Visit, TOC/EOS Visit and unscheduled visit. Shifts (normal, abnormal, not done) from baseline to TOC/EOS Visit will be summarized using patient counts and percentages.

A patient data listing of all physical examination abnormal findings, including findings from unscheduled visits, will be provided.

8.7 Interim analysis

Not applicable

9 CHANGES TO PLANNED ANALYSIS FROM STUDY PROTOCOL

 This SAP v1.0 excludes efficacy analyses from the final analyses due to low number of randomized patients.

11 APPENDICES

Appendix A – Interim Analysis

Not Applicable

Appendix B - Visit Window

Not Applicable
